#### 10.3.6 Sample size and Statistical analysis

Aim# 1 is the primary aim and based on our preliminary data with alpha=.05, a sample size of 20 will give 84% power to detect a relationship with an effect size of  $r=.60$ . The prevalence of PD in industrialized countries is estimated to be about 0.3%. Using this estimation, we anticipate there to be approximately 2,129 persons in the Boise area with PD. Based on these factors we anticipate fully meeting our recruitment needs.

For Aim #1, the goal is to explore the relationship between modifiable factors and outcomes. Initially because of the exploratory nature of these explorations, change scores for the outcome measures will be

constructed. Bi-variate correlations, parametric and non-parametric as appropriate, will be used to assess the strength of the relationship between individual outcome change scores and the modifiable factors. These results may be confounded by the progression of the disease, especially at the later measurement. Change in disease state will be introduced as a possible influence in partial correlations between modifiable factors and outcomes. Effect sizes will be calculate using Cohen's  $d$ .

For Aim #2 the interest is in the reduction of falls among this patient population. Initially to examine the changes in the number of falls a non-parametric McNemar test of change will be used. To examine other factors outside of the intervention that could influence the outcome will follow-up the analyses with McNemar test stratified by possible confounders (i.e. progression of the disease, continuation of the exercise regimen).

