#### 10.3.4 Outcome Measures

Outcome assessments will take place at baseline (i.e., approximately 1 week before the beginning of the training program (T0)), at 6 weeks (T6), and 1 week after the completion of the 12 week training program (T12), as well as 3 months after the training program. All of the outcome assessments up to T12 will be performed by the PI at the Exercise Science Lab while the participants are on their standard course of medication. Motor dysfunction will be assessed at baseline using the motor section of the Unified Parkinson's Disease Rating Scale (UPDRS). The functional balance outcomes include: the mini BEST test (results of which will be shared with trainers at the YMCA for group assignment), the Activities-Specific Balance Confidence (ABC) scale, the Berg Balance Scale (BBS), the Timed Up and Go (TUG), and the Functional Reach Test (FRT). The kinematic outcomes from the hips, knees, and ankles of both limbs will be gathered using the VSTBalance during a straight line gait assessment at a self-selected pace. The infrared camera will identify the length of each lower-extremity segment (femur, tibia, foot) to derive the precise angular displacement (range of motion) occurring at the hip, knee, and ankle joints of each limb.

For Aim #1 we will be assessing the relationship between modifiable factors and outcomes on mobility assessments. We will compare individual characteristics as follows to identify if they are related to the balance outcomes in our model: gait characteristics (stride length, step length etc), motor dysfunction on UPDRS, lower-extremity joint kinematic range of motion, and balance domain dysfunction at baseline. For Aim #2 we will be asking individuals at baseline to self-report the number of falls they have had during the previous 3 months. We will send a prepaid postcard in the mail 3 months after the completion of the training intervention, asking participants to report the number of falls they have experienced since the training ended.

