### 10.3.7 Expected Outcomes

At the completion of this investigation we expect to find that improvements in functional mobility following community-based exercise will be driven by stage of motor dysfunction, peak lower-extremity joint angular displacement, and balance domain dysfunction at baseline (**Aim #1**) (Table 2). These findings will enable a revolutionary approach to rehabilitation for persons with PD, by targeting rehabilitation techniques focused on each individual's modifiable risk factor(s). Finally, we expect to find that by focusing our intervention on the domain of balance dysfunction that is most impaired in individual participants, we will reduce fall incidence (**Aim #2**). This will be a hallmark finding for the treatment of PD, as therapies thus far have been refractory to fall reduction.

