## 10.4 Potential Problems & Alternative Approaches

One potential problem with this clinical trial is that dropouts may occur. Our prior experience with longitudinal exercise studies suggests that we can expect a dropout rate between 5-20%. We have anticipated a very conservative 20% rate, and will recruit 4 additional participants over our sample size of 20. This will ensure an appropriate number of subjects completing the study to maintain the desired statistical power.

While we are attempting to limit the variability in participant outcomes by constraining inclusion criteria to persons with mild to moderate PD, this also poses a challenge in that many participants who volunteer for exercise studies are likely to be physically active individuals, which has the potential to dilute our treatment effect. This recruitment bias may also mean that few of these individuals will have experienced falls at baseline. In the event that non-statistically significant results appear, we have planned our analysis such that we can utilize clinically significant outcomes (eg., effect sizes) to overcome any potential recruitment bias and demonstrate the clinical impact of the intervention.

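### Aim #1 never separates joint motion, gait or balance domain from baseline motor severity, so it cannot show that each factor drives improvement

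*Protocol*

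**What the plan says.** Aim #1 is the primary aim. Protocol 10.3.6 and the identical SAP section describe its purpose in exploratory terms: "the goal is to explore the relationship between modifiable factors and outcomes". The analysis has two steps.

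- Bivariate correlations, parametric or not, "will be used to assess the strength of the relationship between individual outcome change scores and the modifiable factors".
- A follow-up that allows for disease progression: "Change in disease state will be introduced as a possible influence in partial correlations between modifiable factors and outcomes".

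Protocol 10.3.4 lists the candidate factors: gait characteristics, motor UPDRS, lower-limb joint range of motion and balance domain at baseline. It refers to a model, but no multivariable model is specified in either document. On severity it states: "Motor dysfunction will be assessed at baseline using the motor section of the Unified Parkinson's Disease Rating Scale (UPDRS". Hoehn & Yahr stage is recorded at the day-one screening (10.3.3). No later assessment of either scale is described.

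Protocol 10.3.7 expects improvement to be "driven by stage of motor dysfunction, peak lower-extremity joint angular displacement, and balance domain dysfunction at baseline", and foresees rehabilitation aimed at each person's own modifiable risk factors. The first row of Table 2 predicts the greatest gains in people with higher UPDRS scores.

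**The concern.** The plan predicts that baseline severity is related to improvement. If so, any other factor that moves with severity picks up a correlation with improvement from that source, whether or not it contributes anything itself. Motor UPDRS is one of the factors to be correlated with outcome, but it is never a covariate when joint motion, gait or balance domain is examined, and the factors are never entered together.

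The planned partial correlation does not close this gap. How far the disease progresses during follow-up is a different variable from how severe it was at entry. In addition, with UPDRS stated only at baseline and Hoehn & Yahr only at screening, the documents describe no repeat measurement from which the one named covariate could be formed.

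At stake is the reading of the primary aim. Several factors could be reported as drivers when the data reflect one underlying severity gradient, and that reading would feed the targeted rehabilitation foreseen in 10.3.7 and the randomized trial planned in 10.5.

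**Working it through.** **Inputs from the documents.** n = 20, alpha .05 (sidedness not stated), r = .60, power 84% (10.3.6).

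**Inputs assumed.** The correlation b of UPDRS with the change score: .40 or .60. The documents give no value for UPDRS; .60 is borrowed from the power statement. The correlation ρ of the factor with UPDRS: .3, .5 or .7, also not in the documents. The variables are taken as bivariate normal and tests as two-sided.

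**1. The plan's own figure.** The plan says that "based on our preliminary data with alpha=.05, a sample size of 20 will give 84% power to detect a relationship" at r = .60. The critical value is t/√(df + t²) = 2.101/√(18 + 4.414) = .444. Simulation with 400,000 replicates gives power of 83.6%. The bias-corrected Fisher z formula gives Φ{[atanh(.60) + .60/(2×19) − atanh(.444)]×√17} = Φ{(.693 + .016 − .477)×4.123} = 83.1%. The stated 84% is reproduced, for one unadjusted two-sided correlation.

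**2. A factor with no effect of its own.** Its correlation with improvement is then ρ × b. Share of simulated trials (200,000 per cell, n = 20) with p<.05:

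| b | ρ | induced r | bivariate | adjusted for UPDRS |
|---|---|---|---|---|
| .40 | .3 | .12 | 7.9% | 5.0% |
| .40 | .5 | .20 | 13.5% | 5.0% |
| .40 | .7 | .28 | 22.6% | 5.0% |
| .60 | .3 | .18 | 11.7% | 5.0% |
| .60 | .5 | .30 | 25.3% | 5.0% |
| .60 | .7 | .42 | 47.1% | 5.0% |

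The 5% column follows from the set-up: UPDRS is the only confounder and is measured without error.

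**3. Cost of adjusting, if the partial r is .60.** With one covariate the critical value is 2.110/√(17 + 4.451) = .456, and power is Φ{(.693 + .017 − .492)×√16} = 80.9%. On the same formula the unadjusted figure is 83.1%.

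**4. Cost of adjusting, if the bivariate r is .60.** This is the quantity that the protocol powered. With b = .60 as well, partial r = (.60 − .60ρ)/√[(1 − .36)(1 − ρ²)].

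| ρ | partial r | power at n = 20 | n for 84% |
|---|---|---|---|
| .3 | .42/.763 = .55 | 72% | 27 |
| .5 | .30/.693 = .43 | 47% | 44 |
| .7 | .18/.571 = .32 | 27% | 86 |

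**5. Precision.** For an observed partial r of .43 at n = 20 with one covariate, the Fisher z interval is .464 ± 1.96/√16 = −.026 to .954, that is r from about −.03 to .74.

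**The case against.** A reader might infer that each factor is tested by bivariate correlation and nothing else. That is not so: both documents add partial correlations. The gap is that these adjust for progression, not for severity at entry.

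A reader might also infer that the protocol asserts separate effects of each factor. Section 10.3.7 states an expectation, 10.3.6 calls the work exploratory, and 10.5 makes a randomized trial the next step. This stands, and it limits the seriousness of the point. It does not make the planned correlations able to support the driver wording.

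The mechanism is not shown for either named factor. Table 2 words the joint-motion prediction as an increase after exercise, and nothing shows that such an increase follows baseline UPDRS; 10.3.4 leaves the timing open. Balance domain is the type of deficit, one of four, rather than a grade of severity, so the simulated continuous factor does not represent it. Eligibility confined to Hoehn & Yahr 1 to 3 also narrows the severity range. All of this stands. The percentages are therefore illustrations, not estimates for this trial.

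The most substantial objection is cost. The overlap that produces high false-positive rates also weakens the adjusted test, so making adjusted significance a condition would miss many real factors. This too stands, and it argues for reporting the adjusted estimate with its interval rather than using it as a gate.

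**Conclusion.** The concern holds in a limited form. No planned analysis separates joint motion, gait or balance domain from baseline motor severity, although the protocol itself expects severity to predict improvement. The covariate that is named answers a different question and has no described repeat measurement. The plan can show that a factor is associated with improvement; it cannot show that each factor drives it.

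Under the assumed links, a continuous factor that only tracks severity would reach p<.05 in about 8% to 47% of trials of 20, against 5% after adjustment. The range depends wholly on two correlations that the documents do not give.

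The documents do not support the stronger inference that joint motion or balance domain is in fact a proxy for severity, or that a positive finding would be false. Nor do they give a reason to require adjustment for age: nothing in them says that age predicts improvement.

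**What to change.** In protocol 10.3.6 and the SAP:

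- Beside each bivariate r for joint motion, gait and balance domain, report an estimate adjusted for T0 motor UPDRS with its 95% confidence interval. Use a partial correlation for continuous factors and a regression with domain indicators for balance domain.
- Describe a factor as related to improvement beyond severity only with reference to that estimate. Do not make its significance a condition, and do not require age as a covariate.
- State from which measurement change in disease state will be derived.
- In 10.3.7, soften the driver wording to match exploratory, imprecise estimates.

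The adjusted estimates need no new data, because baseline motor UPDRS is already collected; the change is SAP wording and a few lines of code. The statistical cost should be stated openly: about 81% power instead of 84% at a partial r of .60, but only about 72%, 47% or 27% for a factor with a bivariate r of .60 that correlates .3, .5 or .7 with UPDRS (UPDRS link .60). For balance domain, three indicators, UPDRS and an intercept use 5 of 20 degrees of freedom and leave 15.

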## 10.3 Approach

### 10.3.1 Feasibility

The PI has in-depth experience researching kinematic outcomes related to falls in both cross-sectional and longitudinal studies of persons with PD and healthy older adults (Aim #1). Our preliminary studies have recently demonstrated improvements in functional mobility in a small sample of persons with mild-to-moderate PD undergoing this intervention (n=5). A statistically significant improvement was found in the Timed Up and Go (TUG) score (a measure of balance and mobility) from baseline to the mid-point assessment (-2.1 seconds, p=.035). Our preliminary data also demonstrate a clinically meaningful effect of the intervention with an effect size of  $d=0.66$ . Further, our preliminary data also suggests that of these 5 individuals tested thus far, 3 had primary deficits in anticipatory postural control adjustments at baseline according to the miniBEST test. This data will be used to guide our hypothesis-driven Aim #1.

Based on our recent postural control studies following an 18 week rehabilitation program^30 with no participant dropout, no difficulties are expected in recruitment and retention of PD participants for the proposed longitudinal exercise studies.

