Each session will begin with a 10-minute warm-up of breathing and stretching exercises for major muscle groups in the trunk and extremities. This will be followed by a 45- to 60-minute circuit training regimen of function, balance, and non-contact boxing activities that alternate between 3-minute training bouts and 1-minute rest breaks. The functional training will incorporate activities for whole-body fitness and calisthenics, such as push-ups and reaching tasks that are tailored to each participant's capability, along with boxing ring work, which focuses on footwork and agility drills. The balance training activities will focus on tasks in the following areas: quiet stance, anticipatory postural adjustments, reactive postural adjustments, and dynamic

postural control (Table 1). Participants will be placed into groups for this section of the training so that each individual is assigned to work on activities focused on their area of greatest deficiency in the four balance domains. Each domain will be overseen by a specific trainer to ensure safety and continuity of the balance training within each group. The boxing activities will include punching heavy bags, speed bags, and focus mitts. Participants will not make contact with each other while boxing. Participants can pace themselves during the training sessions and take rest breaks as needed. The exercise sessions will end with a 15- to 20-minute cool-down that will emphasize core stretching and breathing exercises.

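### Aim 1 lets a baseline domain factor, apparently read from the miniBEST, be correlated with miniBEST change from that same baseline; the domain claim should rest on TUG, BBS, FRT and ABC change

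*Protocol*

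**What the plan says.** Aim 1 is the primary aim. Protocol 10.3.6 and SAP 10.3.6 carry the same text: "because of the exploratory nature of these explorations, change scores for the outcome measures will be" constructed, and bivariate correlations, parametric or not, are then used "to assess the strength of the relationship between individual outcome change scores and the modifiable factors".

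Protocol 10.3.4 supplies both sides of the correlation.
- **Factors:** gait characteristics, UPDRS motor score, and "lower-extremity joint kinematic range of motion, and balance domain dysfunction at baseline". They are compared to "identify if they are related to the balance outcomes in our model".
- **Functional balance outcomes:** five are listed. The first is "the mini BEST test (results of which will be shared with trainers at the YMCA for group assignment"); the others are ABC, BBS, TUG and FRT.

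Two other places tie the domain factor to the miniBEST. In 10.3.1, of five pilot participants, "3 had primary deficits in anticipatory postural control adjustments at baseline according to the miniBEST test". In 10.3.3, participants are grouped so that "each individual is assigned to work on activities focused on their area of greatest deficiency in the four balance domains". No other instrument is linked to the domains.

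The only adjustment named for Aim 1 is a partial correlation on change in disease state. The plan does not say how the domain factor is scored, which outcome carries the Table 2 domain hypothesis, or that the miniBEST is set aside when the factor comes from it.

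**The concern.** When a factor and a change score use the same baseline measurement, the measurement error of that baseline sits in both. It enters the factor with a plus sign and the change with a minus sign. Someone who scored low at baseline partly by chance will tend to score higher next time, with no training effect. The correlation then reads as worse at baseline, bigger gain.

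Table 2 predicts the greatest improvement in participants with anticipatory (Domain 3) deficits, so for a subscore the artefact runs in the predicted direction. With a single arm there is no control group in which it would show itself. Protocol 10.3.7 wants the results to guide individually targeted rehabilitation, and 10.5 builds a later randomized trial on these aims. A coupled correlation read as responsiveness to training would feed both.

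**Working it through.** **Inputs.** From the documents: n=20, alpha .05, r=.60, power 84% (10.3.6); four domains (10.3.3, Table 1); five functional balance outcomes and four factor groups (10.3.4). Assumptions: reliability .9, .8 or .7 per domain; a total that is the sum of four domain scores with equal variance; true correlation .5 between domains; no true link between baseline and change. Rates come from 40,000 simulated trials per setting, two-sided .05, for which the critical |r| at n=20 is .444.

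**1. The plan's own figure.** Fisher z with bias correction: (atanh .60 + .60/38) × √17 − 1.96 = (.693 + .016) × 4.123 − 1.96 = .96, giving power 83.2%. Exact simulation gives 83.6%. The stated 84% is sound for one two-sided test.

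**2. Subscore against total change, no variation in true change.** Set the observed domain variance to 1, so the error variance is 1−rel.
- Covariance of baseline subscore and total change: −(1−rel).
- Variance of total change: 4 × 2 × (1−rel) = 8(1−rel).
- So r = −√((1−rel)/8).

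**3. The same pair when true change varies.** Let true change have SD 0.5 of the true domain SD, shared across domains. It adds 16 × 0.25 × rel = 4·rel to the variance of total change, so r = −(1−rel)/√(4·rel + 8(1−rel)).

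| Reliability | .9 | .8 | .7 |
|---|---|---|---|
| No variation in true change: r | −.11 | −.16 | −.19 |
| False positives | 7.6% | 10.4% | 12.8% |
| Share in the worse-baseline, bigger-gain direction | 89% | 95% | 98% |
| True change varies: r | −.05 | −.09 | −.13 |
| False positives | 5.4% | 6.8% | 8.6% |
| Share in that direction | 72% | 85% | 92% |

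With no variation in true change, adjusting for an unrelated disease-change covariate leaves 7.3/9.9/12.4%, and Spearman correlation gives 7.1/9.6/11.7%. Neither option in the plan removes the coupling.

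**4. Worst-domain label (Domain 3 yes/no).**
- Against total change: 4.8–5.3% with equal reliabilities, because the baseline errors of the chosen and unchosen domains offset each other in the total. With a reliability gap of .1 between Domain 3 and the rest it is 6–7%; with a gap of .2, 6–11%.
- Against change in that domain's own subscore: about 12/18/23%. Being chosen as worst selects for a low baseline error in that domain.

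**5. Alternatives to the coupled pair.**
- Change on another instrument (TUG-type): about 5% for subscore and label when errors are independent. If same-visit errors correlate .3, the subscore gives 6.0/6.8/7.8%, against 9.8/15.3/20.9% for subscore with total miniBEST change under the same assumption. The label stays at 5.0–5.5%.
- T0 factor against T6-to-T12 miniBEST change: the factor holds the T0 error, the change holds only T6 and T12 errors, so nothing is shared. The rate was 4.8–5.2% for subscore and label, including with error correlation .3 and with unequal reliabilities.

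**6. Scope.** Four factor groups × five outcomes = 20 pairs. If these were independent tests, the chance of any false positive is 1 − .95^20 = 64.2%. With one pair at 7.5% it is 1 − .95^19 × .925 = 65.1%; at 13%, 1 − .95^19 × .87 = 67.2%.

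**The case against.** The strongest reply is that the plan probably means a label. The pilot speaks of primary deficits, the grouping uses the area of greatest deficiency, and Table 2 names a domain. For a label against total change the rate is about 5% under equal reliabilities, and no passage suggests unequal ones. That stands, and it removes most of the problem for the total score. It does not remove it for the domain's own subscore, and a plan built on correlations leaves the numeric coding open.

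It can also be said that Aim 1 is described as exploratory, that its target is phrased as mobility, with TUG as the pilot result, and that Table 2 is never tied to miniBEST change. All true, and a reason for modest weight. But 10.3.4 also speaks of balance outcomes and lists the miniBEST first, so the pair remains available for the domain claim.

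Three stronger readings are tempting and not supported:
- *A positive domain result would be an artefact.* Under the likelier coding and symmetric errors, label against total change is not biased.
- *The artefact favours Domain 3.* With equal errors a subscore affects all four domains alike.
- *Joint range of motion is coupled in the same way.* Protocol 10.3.4 says "The kinematic outcomes from the hips, knees, and ankles of both limbs will be gathered using the VSTBalance" and also lists range of motion as a factor, but it names balance outcomes for the Aim 1 model. No passage specifies baseline range of motion against its own change.

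**Conclusion.** The concern holds as a conditional one of moderate weight. The plan permits a coupled pair and has nothing that would neutralise it. The size rests on assumed reliabilities, on the coding, and on how much true change varies. The upper subscore rates require no variation in true change, which is the extreme case given that the trial expects participants to respond differently. The own-subscore rate for a label matters only if subscore change is analysed, which the plan neither states nor rules out.

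That the factor comes from the miniBEST is an inference, though the documents offer no other source. N and the 84% power do not change, and the overall chance of a false positive hardly moves. The harm lies in how this one pair would be read, because it bears on a stated hypothesis of the primary aim.

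**What to change.** In 10.3.6 of the protocol and SAP:

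1. Rest the Table 2 domain claim on change in the outcomes not scored from the miniBEST: TUG, BBS, FRT and ABC.
2. State whether the domain factor is a miniBEST subscore or a worst-domain label. Report any correlation of that factor with miniBEST total or subscore change from T0 as descriptive and mathematically coupled.
3. As a sensitivity check, correlate the T0 domain factor with T6-to-T12 miniBEST change, which shares no baseline error.

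The cost is wording; every score is already collected. There are three downsides. The miniBEST, the only instrument tied to the trained domains, carries less weight for the domain claim. The T6-to-T12 check covers only the second half of training. And a subscore against TUG-type change still gives about 6–8% if same-visit errors correlate .3, so item 1 reduces the artefact without guaranteeing its removal.

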10.3 Approach

10.3.6 Sample size and Statistical analysis

Aim# 1 is the primary aim and based on our preliminary data with alpha=.05, a sample size of 20 will give 84% power to detect a relationship with an effect size of $r=.60$. The prevalence of PD in industrialized countries is estimated to be about 0.3%.¹ Using this estimation, we anticipate there to be approximately 2,129 persons in the Boise area with PD. Based on these factors we anticipate fully meeting our recruitment needs.

For Aim #1, the goal is to explore the relationship between modifiable factors and outcomes. Initially because of the exploratory nature of these explorations, change scores for the outcome measures will be constructed. Bi-variate correlations, parametric and non-parametric as appropriate, will be used to assess the strength of the relationship between individual outcome change scores and the modifiable factors. These results may be confounded by the progression of the disease, especially at the later measurement. Change in disease state will be introduced as a possible influence in partial correlations between modifiable factors and outcomes. Effect sizes will be calculate using Cohen's d .

For Aim #2 the interest is in the reduction of falls among this patient population. Initially to examine the changes in the number of falls a non-parametric McNemar test of change will be used. To examine other factors outside of the intervention that could influence the outcome will follow-up the analyses with McNemar test stratified by possible confounders (i.e. progression of the disease, continuation of the exercise regimen).

Reference

1. de Lau LM, Breteler MM. Epidemiology of Parkinson's disease. *The Lancet Neurology*. Jun 2006;5(6):525-35. doi:10.1016/s1474-4422(06)70471-9

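### Aim #1 is a set of correlations, but the plan names an undefined Cohen's d as its effect size and plans no confidence interval for r

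*Protocol*

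**What the plan says.** Protocol 10.3.6 and the SAP section of the same number make Aim #1 the primary aim. On sample size they say: "based on our preliminary data with alpha=.05, a sample size of 20 will give 84% power to detect a relationship", the relationship being r=.60, which they call an effect size. For the analysis, change scores are formed for each outcome, and bivariate correlations, parametric or non-parametric, "will be used to assess the strength of the relationship between individual outcome change scores and the modifiable factors". Partial correlations then bring in change in disease state.

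The paragraph closes in the Protocol with "Effect sizes will be calculate using Cohen's" *d*, and in the SAP with "Effect sizes will be calculate using Cohen's d". Neither document says which means are compared, between which time points, or on which SD. Neither mentions a confidence interval for any coefficient.

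Two other places bear on the sentence:

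- **Protocol 10.4** foresees non-significant results and plans to turn to effect sizes in that case, to show that the programme is of clinical value.
- **Protocol 10.3.1** shows how d has been used so far. After a TUG change of -2.1 s (p=.035) from baseline to mid-point in five pilot participants, it reports a "clinically meaningful effect of the intervention with an effect size of" d=0.66.

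**The concern.** The analysis asks whether a factor predicts who improves. The named effect size answers another question: how far two means lie apart in SD units. Most Aim #1 factors in Protocol 10.3.4 are continuous (UPDRS motor score, stride and step length, joint range of motion), and for these d is not the size of the relationship.

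Because the sentence gives no contrast, the analyst can choose one after seeing the data. The most accessible choice in a single-group study is change from baseline, and that is how 10.3.1 appears to use d. Everyone receives the programme, so practice, expectation or regression to the mean could produce a large pre-post d whether or not any factor is related to change. With the fallback in 10.4, a null set of correlations could be followed by a favourable d that does not bear on the primary question. Meanwhile the statistic that does bear on it, r, would appear without its uncertainty, which at n=20 is wide.

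**Working it through.** **1. The plan's own figure.** Inputs from 10.3.6: n=20, alpha=.05, r=.60. Sidedness is not stated; two-sided is assumed.

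The test statistic is t = r√(n−2)/√(1−r²) on 18 df. Under bivariate normality its power is the noncentral t with non-centrality [ρ/√(1−ρ²)]·√W, averaged over W ~ χ² on n−1 = 19 df. The result is 0.836, which rounds to the stated 84%. (The Fisher z approximation gives 0.815; a one-sided test would give 0.904.) So the power figure stands, and it is power for a correlation.

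**2. Precision of r at the planned size.** Fisher z for an observed r=.60:

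- z = atanh(.60) = 0.693; SE = 1/√(20−3) = 0.2425
- limits on z: 0.693 ± 1.96 × 0.2425 = 0.218 and 1.169
- back-transformed: tanh(0.218) = .21 and tanh(1.169) = .82

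A result exactly at the planning value would be compatible with a weak or a very strong relationship.

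**3. Why a pre-post d carries no information on Aim #1.** Let C be the change score, X a baseline factor and S the chosen SD, so that d = mean(C)/S. Add a constant c to everyone's change. The correlation of C with X does not move, because it depends only on deviations from the mean. If S is the baseline SD or the SD of change, it does not move either, and d shifts by c/S. Any value of d can therefore occur with any r, including r = 0.

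**4. How much the denominator can matter: a conditional illustration.** Inputs from 10.3.1: n=5, change -2.1 s, p=.035, d=0.66. Two assumptions are needed that the Protocol does not state: that the p-value is from a paired t-test, and that 0.66 describes this same TUG change.

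| Quantity | p two-sided | p one-sided |
|---|---|---|
| t on 4 df | 3.135 | 2.456 |
| d on SD of change = t/√5 | 1.40 | 1.10 |
| SD of change = 2.1/d | 1.50 s | 1.91 s |

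- SD that makes d = 0.66: 2.1/0.66 = 3.18 s.
- If 0.66 were on the SD of change: t = 0.66 × √5 = 1.476, so p = .21 two-sided (.11 one-sided), not .035.
- Both values can hold at once. With equal SDs before and after, the implied pre-post correlation is 1 − (1.498/3.182)²/2 = .89 (.82 if p is one-sided).

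On these assumptions, the same change is 0.66 or 1.40, a ratio of 1.40/0.66 = 2.1 (1.10/0.66 = 1.7 if one-sided). The difference comes only from the SD used.

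**The case against.** The strongest reply is that the plan already has the right measure. It calls r an effect size and uses correlations to judge strength of relationship, so the coefficients will presumably be reported. That is correct. A reader might infer that the primary aim would be reported without its size; the documents do not support that. What is missing is the interval around r and a meaning for d.

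Second, d may have a legitimate use. One Aim #1 factor, the balance domain most impaired at baseline, can be treated as a grouping, and a standardised mean difference suits a two-group contrast. A correlation can also be converted to d: r=.60 gives 2 × .60/√(1−.36) = 1.5. Both are possible, but the plan states neither. That d will be a pre-post change is likewise an inference, from 10.3.1 and from the single-group design.

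Third, 10.4 speaks of the clinical impact of the programme, not of support for the predictor hypothesis. That is also true, but an uncontrolled pre-post d does not by itself establish clinical impact either.

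Three stronger readings of the pilot should be set aside:

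- **The pilot figures contradict each other.** They do not; step 4 shows that they can both hold.
- **The 0.66 must rest on a between-person SD.** The Protocol names no outcome, interval or denominator for it, and it could belong to another outcome or interval. An exact two-sided Wilcoxon test with five people cannot give p below 2/32 = .0625, which makes a t-test plausible without proving it.
- **The choice of d would mis-size the follow-on trial.** Protocol 10.5 describes a comparison of two active programmes and does not say that this d would size it. A within-group change is not a between-arm effect.

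**Conclusion.** The point holds as a mismatch between the estimand and the named effect size, made worse by the lack of a definition. For the continuous factors, Cohen's d does not measure what Aim #1 tests; its contrast, time point and standardiser are open; and no interval is planned for r, where an observed .60 would run from .21 to .82. This rests on the text of 10.3.6, the SAP and 10.4, and on the usual Fisher approximation. It does not depend on the pilot.

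The pilot adds only an example: under a paired t-test and a shared TUG change, d is 0.66 on one SD and 1.40 (1.10 if p is one-sided) on another.

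The 84% power is not affected and the planned correlations remain usable. The sponsor should make the change before analysis, because the fallback in 10.4 gives an undefined d most influence when the planned tests are not significant.

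**What to change.** In Protocol 10.3.6 and the SAP, replace the Cohen's d sentence with the following:

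- For every Aim #1 factor-outcome pair, report r (or rho) with its 95% confidence interval, whether or not it is significant.
- Report mean T0 to T12 change for each outcome in its original units with a 95% confidence interval, labelled descriptive.
- If d is also given, state the contrast and time points, and use one prespecified standardiser for all outcomes. The T0 SD is one option; the need is to fix one in advance. If d is meant for the balance-domain grouping, name the groups compared.

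In 10.3.6 and 10.4, add that an uncontrolled pre-post d is not evidence for Aim #1 and does not by itself show an effect of the intervention.

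The cost is a few sentences and routine output; no data collection or sample size changes. The drawback for the sponsor is that the reported effects will look less precise.
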